7.6 Variables for Safety Analysis

Safety evaluations include AEs/SAEs/AESIs, clinical laboratory parameters (hematology, serum chemistry, serum immunoglobulin (IgG, IgM, IgA), CRP), and ECG. Laboratory parameters cover parameters of serum chemistry, hematology, quantitative immunoglobulins (IgA, IgG, IgM), and CRP. More details are in the parts 7.1 and 7.2, see above. For ECG, the frequencies of 'Normal or not clinically significant' or 'Clinically significant' will be calculated.

The severity of AEs will be graded using the NCI-CTCAE version 5.0 dictionary. An AE is defined as any event arising or worsening after start of study drug administration until 110 days (based on five times the half-life of Rituximab and Pembrolizumab) after the last study drug intake. All AEs, drug related AEs, serious AEs will be summarized by MedDRA classification (SOC and preferred term) and worst CTCAE grade. Additionally, adverse events of special interest (AESIs) will be analysed as a separate category.

Adverse events (AE), serious adverse events (SAE) adverse events of special interest (AESI): Following variables will be used in the analysis of AEs, SAEs and AESI: *SUBJECTID*, *AESPID*, *AETERM*, *AETOXGR*, *AERELPEM*, *AERELRIT*, *AEACNPEM*, *AEACNRIT*, *AESER*, *AESI*, *AESS*, *AESSCAS*, *AESTDAT*, *AEOUT*, and *AEENDAT* in table *AE*. For the analysis of AEs, the final outcome will be analysed only. AEs, SAEs (variable *AESER* in table *AE*) and AESIs (variable *AESI* in table *AE*) will be analysed separately. Additionally, AEs / SAEs / AESIs of grade ≥ 3 (variable *AETOXGR* in table *AE*) will be analysed separately.

Concomitant medication: Concomitant medication is documented during treatment period. Variables for analysis are *SUBJECTID*, *CMSPID*, *CMTRT*, *CMINDC*, *CMDSTXT*, *CMFREQ*, *CMROUTE*, *CMROUTEOTH*, *CMSTDAT*, *CMONGO*, and *CMENDAT* in table *CM*.

7.7 Further Variables

For the analysis of treatment duration, the difference between the last day of treatment (variable *EXENDAT_ET* in table *DSET*) and first day of treatment (variable *EXSTDAT* for *ACTIVITYID* = 'C1D1_SV' in table *EX1*) will be analysed. For the analysis of study duration, the difference between time of registration (date of patient signed written informed consent; variable *RFICDAT* in table *DM*) and date of EOS (variable *DSEOSENDAT* in table *DSEOS*; in case of loss of contact: variable *DSLSTDAT_EST* in table *DSEOS*) will be analysed.

For the analysis of extranodal involvement, the frequencies (yes/no/not assessable) of bone marrow infiltration and splenomegaly will be analysed using the variables *PRSNT_IBM* and *PRSNT_SPLMG* in table *ENI*.

For analysis of the lymph node status the total number of affected lymph nodes (all regions) will be calculated as sum of the variables *PRSNT_CEL*, *PRSNT_CER*, *PRSNT_CLL*, *PRSNT_CLR*, *PRSNT_AXL*, *PRSNT_AXR*, *PRSNT_MED*, *PRSNT_HIL*, *PRSNT_HIR*, *PRSNT_PER*, *PRSNT_TC*, *PRSNT_PAR*, *PRSNT_SPH*, *PRSNT_HOL*, *PRSNT_MES*, *PRSNT_ILL*, *PRSNT_ILR*, *PRSNT_IGL*, *PRSNT_IGR*, and *LNSOTHNUM* in table *LNS*.

For analysis of toxicity, all patients with a delay of treatment due to toxicity (variable *EXTDEL_TOX* = 1 in table **EX2**) will be listed. Additionally, the frequency of these patients will be calculated separate for Pembrolizumab and Rituximab (variables *EXTDELSPY1* and *EXTDELSPY2* in table **EX2**).

For analysis of study drug administration, the percentage (from scheduled dose) of study drug administered will be calculated (variables *EXPEMORRES* and *EXRITORRES* in table **EX1**). Additionally, all patients with deviations in study drug administration will be listed (variable *EXIAYN* = 1 in table **EX1**).

8 Statistical Methods

8.1 Methods for Descriptive Statistics

Continuous variables:

Continuous variables will be summarised using the following standard descriptive summary statistics (if appropriate): number of observations, number of missing observations arithmetic mean, standard deviation, minimum, lower quartile, median, upper quartile, maximum. Furthermore, graphical methods will be used, e.g. Boxplots, plots of time course of mean \pm standard deviation resp. median \pm $\frac{1}{2}$ inter quartile range, Kaplan-Meier plots for variables of the secondary endpoint as appropriate. In case of too few measurements, the single measured values will be displayed.

Categorical variables:

Categorical data will be described using absolute and relative frequencies. In case of too few measurements, the single measured values will be displayed. Missing data will be treated as separate category in statistical analysis.

8.2 Details of Statistical Analysis

8.2.1 Efficacy Analysis of the Primary Endpoint

The primary endpoint (CRR) will be evaluated after end of treatment (18 cycles) after the last recruited patient has started her/his treatment. The primary parameter CRR will be evaluated in a modified intention to treat way, which means that all patients for whom the primary endpoint CRR is measured after end of treatment will be included in the analysis of the primary endpoint (Core Analysis Population, see CTP subsection 12.6.1). Patients without staging at regular end of treatment will be defined as non-responder. Only patients who withdraw will be excluded. The results on efficacy in the Core Analysis Population were considered to be the main efficacy results (confirmatory results). The one sample exact binomial test will be used for the analysis of the primary endpoint to test the CRR against the fixed value 56% at the 2.5% significance level (one-sided). Thus, the decision about the new concept will be based on a statistical test of the form: $H_A: \{CRR > 56\% \}$ vs. $H_0: \{CRR \leq 56\% \}$.

Patients who withdraw will be included in a separate explorative analysis. Additionally, a one-sided 97.5% confidence interval for CRR will be calculated as an effect estimator.

A separate exploratory sensitivity analysis of the primary endpoint will be done to investigate the influence of withdrawals.

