5.2 Primary Endpoint

Primary endpoint is the complete response (CR rate (CRR) determined after end of treatment (18 cycles). Patients who progress before EOT will be treated as CR='NO' and will be included in the calculation of the primary endpoint. No primary endpoint will be determined for patients who withdraw. These patients will be excluded from the confirmatory data analysis but will be analyzed in a separate exploratory sensitivity analysis of the primary endpoint.

For further information about the statistical analysis of the primary endpoint, see section 12.

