10.1 Informed consent

All subjects must sign and date the most current IRB/IEC approved informed consent form. It is the responsibility of the investigator or a designated physician who is part of the study team to obtain informed consent in compliance with national requirements from each subject prior to any study related procedures or, where relevant, prior to evaluating the patient's suitability for the study.

The informed consent document used by the investigator for obtaining subject's informed consent must be reviewed and approved by the sponsor prior to IRB/IEC submission.

The investigator must explain to a potential patient the aims, methods, reasonable anticipated benefits and potential hazards of the trial and any discomfort it may entail. Patients will be

informed that they are free not to participate in the trial and that they may withdraw consent to participate at any time. They will be told which alternative treatments are available if they refuse to take part and that such refusal or withdrawal will not prejudice future treatment.

Confirmation that the informed consent form has been signed should occur before any study-specific procedures are performed and before patient registration. All subjects who receive protocol-specified therapy or specified treatment should be re-informed and should re-consent with at least every safety relevant updated version of the IRB/IEC approved informed consent form during study participation as applicable and per institutional guidelines.

Withdrawal in case the patients experiences an adverse event which indicates to the investigator that continued participation is not in the best interest of the patient is performed by the investigator. All data collected before the time point of withdrawal remain within the study database (according to AMG §40 (2a) 3) Consent will be sought from the patient, in order to be allowed to

- report further major outcome information (e.g. efficacy data)
- guarantee the safety of a patient
- comply with requirements to submit complete documents for authorisation

Documentation that informed consent occurred prior to the study subject's entry into the study and of the informed consent process should be recorded in the study subject's source documents including the date.

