10.4 Criteria for premature discontinuation of the study

10.4.1 Early Treatment discontinuation for an individual patient

Per-protocol treatment of the patient must be discontinued for the following reasons:

- pregnancy
- disease progression at any time
- intercurrent illness that would, in the judgment of the Investigator, affect assessment of clinical status to a significant degree
- recurrent Grade 2 pneumonitis
- repeated clinically relevant violation of the protocol
- non-compliance by the patient with protocol requirements
- excessive and unexpected toxicity of the treatment
- patient's decision to stop her/his participation in the trial or study treatment
- decision by the treating physician for medical reasons
- discontinuation of the whole study at the request of sponsor
- Patient is lost to follow-up. If a patient does not return for scheduled visits, every effort should be made to re-establish contact. In any circumstance, every effort should be made to document patient outcome, if possible.

In summary, a patient should be withdrawn from the trial treatment if, in the opinion of the investigator, it is medically necessary, or if it is the wish of the patient.

The reason for the early termination of the per-protocol treatment must be documented and the 'Coordinating Investigator' must be informed in written form e.g. on the respective eCRF. Patients who stop per-protocol therapy early must be documented and followed-up according to protocol. Early termination should be avoided. In case of an early termination of therapy, reasons / circumstances and if applicable the final disease status of the patient have to be

documented. **If the patient does not withdraw the consent for further follow-up, he or she should be followed-up as planned.**

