10.4.2 Early study termination for an individual patient

The only reason for the exclusion of a patient from the study is his or her withdrawal of consent. Patients can withdraw their informed consent to this study at any time and this does not interfere with their right of treatment by the local investigator (physician). In case of cessation of the study-treatment a final statement concerning the treatment effect and the causes of premature study-termination have to be given by the local investigator.

In case it becomes evident *ex post* that a patient did not qualify for the study (e. g. did not fulfill all inclusion criteria nor had an exclusion criterion at the time of registration) the physician treating the patient with *ex-post* non-qualification will be informed by the Clinical Trial Office Ulm on the *ex post* non-qualification of a patient. A thorough benefit risk assessment has to be performed by the investigator together with the sponsor to decide if the patient with *ex-post* non-qualification should continue study treatment and the result has to be documented. The patient with *ex post* non-qualification is only allowed to continue study treatment if it is concluded that in this case for the patient benefits will outweigh risks. The documentation and follow up of patients with *ex post* non-qualification must continue as planned in the protocol, because the documentation of such patients is not different from the documentation of qualified patients.

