12.2 Sample Size

For sample size calculation the one-sided one sample exact binomial test was used. According to the above data, the CRR for the total group of the different subtypes of MZL must be better than 56% after end of treatment (18 cycles). Anticipating a CRR for Pembrolizumab/Rituximab of about 75%, a significance level of 2.5% (because of one-sided test) and a power of 80%, 48 full evaluable patients will be necessary to show that the combination will be a promising candidate for challenging immuno-chemotherapy (PROC POWER, SAS 9.3; 48 patients is the first number of patients with a stable power of more than 80%). It is expected, that the rate of withdrawal in the study is smaller than 15%. According to these parameters, the study will enrol 56 subjects. The distribution between the sexes is not relevant, because neither incidence of MZL is differed between sexes nor clinically outcome measures such as response, progression free and overall survival has been shown to be related to sexes.

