7.3 End of treatment

For evaluation of the end of treatment, the frequencies (yes/no) for the question "Was study medication in treatment period applied?" will be calculated. The date of last application and the reason (variables *EXENDAT_ET* and *EXREASND_ET* in table *DSET*) will be listed. Additionally, the frequencies for the primary reasons for termination will be calculated and listed (variable *DSDECOD_ET* in table *DSET*). The specifications for termination and the date of progression and

the date will be listed (variables *DSAESPY_ET* and *RSDAT_ET* in table *DSET*). Additionally, the date of last contact and the specification will be listed (variables *DSLSTDAT_ET* and *DSTERM_ET* in table *DSET*). Furthermore, the frequency of specification (Refusal of further study treatment/Withdrawal of consent) and status of patient (Patient continues with follow-up/Patient discontinues study) will be calculated (variables *DSDECOD_ET2* and *DSCONT_ET* in table *DSET*).

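### The confirmatory CRR excludes patients who 'withdraw' without defining the term, and the SAP 7.5 derivation never codes unstaged patients as non-responders; with 22 patients this can change the test result

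*SAP*

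**What the plan says.** **Who is excluded.** Protocol 5.2 states: "No primary endpoint will be determined for patients who withdraw". Protocol 12.3 and SAP 4, 6 and 8.2.1 repeat the exclusion. None of them says what counts as withdrawing.

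**Who counts as a non-responder.** Protocol 12.6.1 and SAP 4, 6 and 8.2.1 class patients without staging at the regular end of treatment as CR 'NO'. SAP 8.2.1 puts the two rules side by side: "Patients without staging at regular end of treatment will be defined as non-responder. Only patients who withdraw will be excluded".

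**How the protocol uses the word.**
- 10.1 assigns one kind of withdrawal to the investigator: "Withdrawal in case the patients experiences an adverse event which indicates to the investigator that continued participation is not in the best interest". The same section covers patients withdrawing consent.
- 10.4.1, on stopping treatment: "a patient should be withdrawn from the trial treatment if, in the opinion of the investigator, it is medically necessary", or if the patient wishes it.
- 10.4.2, on leaving the study: "The only reason for the exclusion of a patient from the study is his or her withdrawal of consent".

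**How the variable is derived.** When the end-of-treatment tumor assessment is missing (RSPERF = 0), SAP 7.5 speaks only of patients who withdraw. CR can then be determined only if progression was documented earlier; otherwise CR_yes_no stays missing. No line sets CR_yes_no to 0 for an unstaged patient who did not withdraw.

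**What is recorded.** SAP 7.3 tabulates "the frequency of specification (Refusal of further study treatment/Withdrawal of consent") from DSDECOD_ET2. A separate variable, DSCONT_ET, shows whether the patient continues follow-up or leaves the study. Neither is linked to the exclusion rule.

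**Sensitivity analysis.** SAP 8.2.5 plans two exploratory scenarios: all withdrawals set to CR 'no', and all set to CR 'yes'.

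**The concern.** Take a patient whom the investigator takes off for an adverse event and who has no staging at the regular end of treatment. The non-responder rule keeps this patient in the denominator as CR 'NO'. If Protocol 10.1 makes the patient a withdrawal, the exclusion rule removes the same patient. A programmer who follows SAP 7.5 literally finds no instruction that produces CR 'NO'.

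The choice has a direction. Removing someone who would count as a non-responder turns x/N into x/(N-1), so the rate can only rise. If intolerance of the combination is a reason for leaving, poorer tolerability would raise the reported CRR. This is the denominator of the only confirmatory test, and with 22 patients two or three classifications can decide it.

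**Working it through.** **Inputs.** The SAP 8.2.1 test is an exact binomial test "to test the CRR against the fixed value 56% at the 2.5% significance level (one-sided"). Enrolment was 22 of 56 planned (SAP 2.1); I take all 22 as treated. Protocol 12.2 expects withdrawal below 15%. The documents give neither the number of withdrawals nor their CR status, so 5%, 10% and 15% are an assumed range.

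**The plan's own figure.** Protocol 12.2 states "a significance level of 2.5% (because of one-sided test) and a power of 80%, 48 full evaluable patients will be necessary", for 75% against 56%. The cut-off r is the smallest value with P(X ≥ r | n, 0.56) ≤ 0.025. At n = 48, r = 35, with exact level 1.2% and power 69.9%, so the stated 80% is not reproduced. Against the unrounded historical 55.8%, r = 34 and power is 80.0%, which is probably where 48 comes from. This does not affect the present point.

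**Cut-offs near the actual size.**

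| n analysed | CRs needed | exact level |
|---|---|---|
| 22 | 18 | 1.07% |
| 21 | 17 | 1.58% |
| 20 | 16 | 2.33% |
| 19 | 16 | 0.97% |

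Success needs 18 CRs with nobody excluded, but 16 if two or three are excluded.

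**Effect on the rate.** Let w be the share excluded and c the CR rate among them. With a true CRR of 56% over all treated patients, the rate among those kept is p = (0.56 - w·c)/(1 - w). For c = 0:
- w = 5%: 0.56/0.95 = 58.9%
- w = 10%: 0.56/0.90 = 62.2%
- w = 15%: 0.56/0.85 = 65.9%

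**Effect on the false-positive rate, 22 treated.** Each patient is excluded with probability w. The rate is the sum over k of P(k excluded) × P(X ≥ r(22-k) | 22-k, p).

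| excluded patients' CR rate | w = 5% | w = 10% | w = 15% |
|---|---|---|---|
| 0 (all non-CR) | 2.9% | 5.5% | 9.6% |
| 28% (half the null rate) | 2.1% | 3.1% | 4.2% |
| 56% (unrelated to response) | 1.5% | 1.6% | 1.6% |

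**Fixed numbers of excluded non-CR patients.** Those kept have CR rate 0.56 × 22/(22 - k). The false-positive rate is 2.8% for one excluded, 6.8% for two, 5.8% for three and 13.2% for four. It is not monotone because the cut-off moves in whole patients.

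**A concrete case.** Suppose 16 CRs and three withdrawals without CR. Excluded: 16/19 = 84%, P(X ≥ 16 | 19, 0.56) = 0.0097, success. Kept as non-responders: 16/22 = 73%, P(X ≥ 16 | 22, 0.56) = 0.084, no success.

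**The case against.** The strongest reply is that the protocol separates stopping treatment from leaving the study. Section 10.4.1 concerns treatment only and asks that patients who stop early be followed as planned unless they withdraw consent for follow-up. Section 10.4.2 makes withdrawal of consent the sole reason for exclusion from the study. On that reading toxicity stoppers stay in. This largely stands: their exclusion is possible, not established, and rests on one sentence in Protocol 10.1.

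A reader might also infer more than the documents support:
- *That SAP 7.5 settles the matter towards exclusion.* Its missing-assessment text is about withdrawals and does not say that a toxicity stop is one. It conflicts with SAP 4, 6 and 8.2.1; it does not override them.
- *That the form merges refusal of treatment with withdrawal of consent.* SAP 7.3 lists them as distinct values.
- *That a toxicity stopper is necessarily unstaged.* Protocol 9.3 provides an early-termination visit with tumor assessment 4-8 weeks after the last dose, and Appendix A has one combined EOT/ET column. If a CR at that visit counts, excluding that patient would not inflate CRR.
- *That the error rate is about 19%.* At n = 48 with p = 65.9%, P(X ≥ 35) is 19.2%, but this is a worst case at a sample size that was not reached.

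Finally, the two scenarios in SAP 8.2.5 will show how far the result depends on withdrawals. That also stands, but they are exploratory and leave the confirmatory decision unchanged.

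**Conclusion.** The concern holds in a conditional form. Two defects are in the text itself: the exclusion criterion is undefined while Protocol 10.1 allows a reading that takes in adverse-event withdrawals, and SAP 7.5 does not implement the non-responder rule stated in SAP 4, 6 and 8.2.1. The second defect remains even if withdrawal means consent only.

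The size depends on facts that the documents do not give. At 22 treated and 5-15% excluded, the false-positive rate runs from about 1.5% (exclusion unrelated to response) to 9.6% (15% excluded, all non-CR). It exceeds 2.5% at each of these shares if all excluded are non-CR, and from the 10% share if they have half the null CR rate. The documents do not show that toxicity stoppers will be excluded, or that inflation has occurred. They do leave open a choice that can reverse the result.

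**What to change.** **Minimum.**
- In SAP 4, 6, 7.5 and 8.2.1, define withdrawal as withdrawal of consent, identified by that value of DSDECOD_ET2.
- In the SAP 7.5 code, set CR_yes_no = 0 for every other patient without staging at the regular end of treatment, including toxicity stops and refusal of further treatment.
- State whether an early-termination assessment counts for the primary endpoint.

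The cost is SAP wording and a few lines of code. Since the SAP already records the last end-of-treatment visit (06 Dec 2024), the clarification should be dated and made before the primary analysis is run.

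**Preferred.** Report the first scenario of SAP 8.2.5 (withdrawals set to CR 'NO') as the main result, and keep the analysis excluding withdrawals and the all-'yes' scenario as sensitivity analyses. This departs from Protocol 5.2 and 12.3, so SAP 3 should document it as a change from the protocol. SAP 8.2.5 plans these scenarios but does not show that they are already programmed. The reported CRR may be slightly lower.

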8.2.2 Sample Size Calculation

Full details of the sample size calculation are in the CTP at pages 13 and 92.

8.2.3 Efficacy Analysis of Secondary Endpoints

All secondary endpoints (Response rate, Best response, Time to best response, Time to first response, PFS, TTF, DR, CSS, OS and Quality of life during trial (therapy)) will be analysed exploratory by respective descriptive analysis, statistical tests and two-sided 95%-confidence intervals. Missing values will not be replaced.

Response rate and best response: The rates incl. the two-sided 95% confidence intervals (Clopper-Pearson) will be provided. The confidence limits can be used for a comparison with a fixed value.

Time to best response, time to first response, PFS, TTF, RD, CSS, OS: Kaplan-Meier plots will be provided. Because time to best response and time to first response describe a favourable event, the ordinate of the Kaplan-Meier plot will be "1 minus survival probability" instead "survival probability".

Quality of life during trial: The FACT-Lymphoma Trial Outcome Index (TOI), the FACT-G total score, the FACT-Lymphoma total score and the sum score for each of the five subscales (PWB, SWB, EWB, FWB, LYMS), will be analysed as continuous variable.

With exception of the efficacy analysis of the primary endpoint, each statistical test will be performed two-sided at a significance level of 5%. All results from these analyses will be regarded as hypothesis generating only and not as proof of efficacy.

